##### 14.1.2.3. All Enrolled Population

The all enrolled population will consist of all patients who receive an IV infusion of AVXS-101. Analyses of endpoints in this population are considered descriptive.

#### 14.1.2.4. Safety Population

The safety analysis population will consist of all patients who receive an IV infusion of AVXS-101. All safety analyses will be conducted on the safety analysis population.

### 14.2. Sample Size Calculation

This is a pivotal Phase 3, open-label, single-arm, single-dose, study assessing the efficacy and safety of AVXS-101 (gene replacement therapy) in up to twenty (20) patients with spinal muscular atrophy (SMA) Type 1 who meet enrollment criteria, may be either symptomatic or pre-symptomatic and are genetically defined by no functional survival motor neuron 1 gene (*SMN1*) with 1 or 2 copies of survival motor neuron 2 gene (*SMN2*) and who are < 6 months (< 180 days) of age **at the time** of gene replacement therapy (Day 1). Enrolling up to twenty (20) patients under the broader enrollment criteria is projected to enable enrollment of at least fifteen (15) patients that meet the Intent-to-Treat Population (ITT) criteria. The ITT population is identified as symptomatic patients with bi-allelic *SMN1* deletions and 2 copies of *SMN2* without the *SMN2* gene modifier mutation (c.859G>C) and will comprise the primary population for evaluation of the primary and secondary endpoints. Study power is based upon efficacy analysis of the ITT population. Furthermore, the first three patients enrolled must meet criteria for the Intent-To-Treat Population to enable a comparison of CHOP-INTEND scores at one-month following gene replacement therapy to enable a comparison of patient response between AVXS-101-CL-303 patients and Cohort 2 patient results from the Phase 1 trial (AVXS-101-CL-101). Patients with 1 copy of *SMN2*, pre-symptomatic patients and patients with the *SMN2* gene modifier mutation (c.859G>C) and other permutations outside of those specified in the ITT population will be evaluated separately as part of additional subgroup analyses. Details of all analyses will be contained within the Statistical Analysis Plan.

The two co-primary efficacy endpoints will be assessed in sequence: The endpoint of functional independent sitting will be assessed first and, only if this assessment meets statistical significance will the endpoint of survival be assessed.

Based upon the widely cited natural history of the disease (Pediatric Neuromuscular Clinical Research Network [PNCr]) [*Neurol.* 2014; 83(9):810-817], it is expected that no patients in this population would be expected to attain the ability to sit without support or accomplish other milestones (rolling over, standing, walking) prior to 18 months of age. Assuming that the true response rate for the primary endpoint is actually zero (or as low as 0.1%) in the population of interest of the historical control, the first co-primary efficacy endpoint hypothesis:

$$\begin{aligned} H_0: p_{AVXS-101} &= 0.1\% \\ &\text{versus the alternative} \\ H_a: p_{AVXS-101} &> 0.1\%, \end{aligned}$$

where  $p$  is the proportion of functional independent sitting for at least 30 seconds at the 18 months of age study visit.

Based upon preliminary results from the ongoing Phase 1 clinical study AVXS-101-CL-101, at least 40% of treated symptomatic patients with bi-allelic deletions of *SMN1* and 2 copies of *SMN2* without the *SMN2* gene modifier mutation (c.859G>C) are expected to achieve the co-primary efficacy endpoint of functional independent sitting for at least 30 seconds at the 18 months of age study visit. With the assumption for the true response rate of AVXS-101 for the

primary endpoint being in the range of 30% - 40%, a sample size of 15 patients that meet ITT criteria will be enrolled and assuming approximately 30% of patients are excluded from analysis, would yield an ITT population that would provide power of > 90% to detect a significant difference from 0.1% with  $\alpha = 0.025$  using a 1-sided exact test for a binomial proportion.

The second co-primary efficacy endpoint hypothesis:

$$H_0: p_{AVXS-101} = p_{HISTORICAL-FINKEL}$$

*versus the alternative*

$$H_a: p_{AVXS-101} \neq p_{HISTORICAL-FINKEL}$$

where  $p$  is the proportion of patients surviving at 14 months of age.

Based upon preliminary results from the ongoing Phase 1 clinical study AVXS-101-CL-101, at least 80% of treated symptomatic patients with bi-allelic *SMN1* deletions and 2 copies of *SMN2* without the *SMN2* gene modifier mutation (c.859G>C) are expected to achieve the co-primary efficacy endpoint of survival through 14 months of age. It is anticipated that 75% of patients in the PNCR population would not survive beyond 13.6 months of age, and that these control patients will represent a 25% survival rate based upon the natural history of the disease. With this efficacy, an enrolled sample size of 15 patients that meet ITT criteria (assuming 30% of patients are excluded from the analysis) would yield an ITT population that would provide power of > 80% to detect a significant difference from the historical control with  $\alpha = 0.05$  using a 2-sided Fisher's Exact test, comparing to the 26 age and gender matched patients from a published natural history observational study performed at 3 large, tertiary care centers in the United States (Harvard University, Columbia University, Children's Hospital of Philadelphia; PNCR).

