whether the AVXS-101 treated patients achieve a response rate greater than 0.1%. Based upon preliminary results from the ongoing Phase 1 clinical study AVXS-101-CL-101, at least 40% of treated patients in the ITT population are expected to achieve the co-primary efficacy endpoint of functional independent sitting for at least 30 seconds at the 18 months of age visit. With the assumption for the true response rate of AVXS-101 for the primary endpoint being in the range of 30% - 40%, a sample size of 15 patients that meet ITT criteria will be enrolled and assuming approximately 30% of patients are excluded from analysis, would yield an ITT population that would provide power of > 90% to detect a significant difference from 0.1% with  $\alpha = 0.025$  using a 1-sided exact test for a binomial proportion.

The second co-primary efficacy endpoint of survival at 14 months of age will be evaluated by comparing the results observed in the ITT population with the results from the age and gender-matched control patients selected from existing natural history data sets (PNCr) [*Neurol.* 2014; 83(9):810-817]. It is anticipated that 75% of patients in the PNCr population would not survive beyond 13.6 months of age, and that these control patients will represent a 25% survival rate based upon the natural history of the disease. Based upon preliminary results from the ongoing Phase 1 clinical study (AVXS-101-CL-101), at least 80% of patients in the ITT population are expected to survive, as defined, through 14 months of age. With this efficacy, an enrolled sample size of 15 patients that meet ITT criteria (assuming 30% of patients are excluded from the analysis) would yield an ITT population that would provide power of > 80% to detect a significant difference from the historical control with  $\alpha = 0.05$  using a 2-sided Fisher's Exact test.

9.2.1.	Prophylactic Administration of Prednisolone.....	37
9.2.2.	Prohibited Medications.....	38
9.3.	Treatment Compliance.....	38
9.4.	Randomization and Blinding.....	38
10.	STUDY PRODUCT MATERIALS AND MANAGEMENT.....	39
10.1.	Study Product.....	39
10.2.	Study Product Dose and Dose Justification.....	39
10.3.	Study Product Packaging and Labeling.....	39
10.4.	Study Product Storage.....	39
10.5.	Study Product Preparation.....	40
10.6.	Study Product Administration.....	40
10.7.	Dose Adjustment Criteria.....	40
10.8.	Study Product Accountability.....	40
10.9.	Study Product Handling and Disposal.....	40

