### 5.1. Background

Spinal muscular atrophy is a neurogenetic disorder caused by a loss or mutation in the survival motor neuron 1 gene (*SMN1*) on chromosome 5q13, which leads to reduced SMN protein levels and a selective dysfunction of motor neurons. Spinal muscular atrophy is an autosomal recessive, early childhood disease with an incidence of approximately 1:10,000 live births [1]. Spinal muscular atrophy is the leading cause of infant mortality due to genetic diseases. Disease severity and clinical prognosis depends on the number of copies of survival motor neuron 2 gene (*SMN2*). In its most common and severe form (Type 1), hypotonia and progressive weakness are recognized in the first few months of life, leading to diagnosis before 6 months of age and early death due to respiratory failure before 2 years of age. Motor neuron loss in SMA Type 1 is profound in the early post-natal period (or may even start in the prenatal period), whereas motor neurons in SMA Type 2 and Type 3 patients adapt and compensate during development and persist into adult life. The findings from various neurophysiological and animal studies have shown an early loss of motor neurons in the embryonic and early post-natal periods [2,3,4]. From a clinical perspective, these findings emphasize the importance of first targeting the SMA Type 1 group for gene transfer of *SMN1* in hopes of rescuing neurons at this critical stage. The goal in continuing the development plan for AVXS-101 is to modify the SMA Type 1 phenotype, which will hopefully lead to a milder disease course and prolonged survival as seen in SMA Type 2 and Type 3 patients.

Therapeutic efforts in SMA have focused on the potential for small molecules to increase SMN levels. These include deacetylase inhibitors, such as, valproic acid, sodium butyrate, phenylbutyrate, and trichostatin A. These agents activate the *SMN2* promoter, resulting in increased full-length SMN protein in SMA animal models [5,6]. However, clinical studies employing several of these agents, most notably phenylbutyrate, valproic acid, and hydroxyurea,

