### 8.2. Patient Exclusion Criteria

Patients must not meet any of the following exclusion criteria:

1. Previous, planned or expected scoliosis repair surgery/procedure during the study assessment period
2. Pulse oximetry < 96% saturation at screening while the patient is awake or asleep without any supplemental oxygen or respiratory support, or for altitudes > 1000 m, oxygen saturation < 92% awake or asleep without any supplemental oxygen or respiratory support  
Pulse oximetry saturation may decrease to < 96% after screening provided that the saturation does not decrease by  $\geq 4$  percentage points
3. Tracheostomy or current use or requirement of non-invasive ventilatory support averaging  $\geq 6$  hours/day over the 7 days prior to the screening visit; or  $\geq 6$  hours/day on average during the screening period or requiring ventilatory support while awake over the 7 days prior to screening or at any point during the screening period prior to dosing
4. Patients with signs of aspiration/inability to tolerate non-thickened liquids based on a formal swallowing test performed as part of screening. Patients with a gastrostomy tube who pass the swallowing test will be allowed to enroll in the study

5. Patients whose weight-for-age is below the third percentile based on World Health Organization (WHO) Child Growth Standards [26]
6. Active viral infection (includes human immunodeficiency virus [HIV] or positive serology for hepatitis B or C, or Zika virus)
7. Serious non- respiratory tract illness requiring systemic treatment and/or hospitalization within 2 weeks prior to screening
8. Upper or lower respiratory infection requiring medical attention, medical intervention, or increase in supportive care of any manner within 4 weeks prior to screening
9. Severe non-pulmonary/respiratory tract infection (e.g., pyelonephritis or meningitis) within 4 weeks before administration of gene replacement therapy or concomitant illness that, in the opinion of the Principal Investigator, creates unnecessary risks for gene replacement therapy such as:
  - a. Major renal or hepatic impairment
  - b. Known seizure disorder
  - c. Diabetes mellitus
  - d. Idiopathic hypocalcuria
  - e. Symptomatic cardiomyopathy
10. Known allergy or hypersensitivity to prednisolone or other glucocorticosteroids or their excipients

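### The survival comparator is matched on an undefined age and on gender, and controls are not required to be alive and free of permanent ventilation at the dosing age

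*Protocol*

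**What the plan says.** Protocol Section 14.2 describes the second co-primary test as "comparing to the 26 age and gender matched patients from a published natural history observational study", using a two-sided Fisher's exact test at 0.05. The Synopsis (Statistical Methods) gives the same two factors: "comparing the results observed in the ITT population with the results from the age and gender-matched control patients". Section 14.3.2 speaks of matched patients and names no factor. Section 14.1.1 adds a general statement that the historical controls are comparable to the target population, but lists no criterion.

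On the control rate, Section 14.2 expects three quarters of the PNCR population not to survive beyond 13.6 months of age, so that "these control patients will represent a 25% survival rate based upon the natural history of the disease". With 80% survival on treatment and 15 ITT patients less 30%, it claims "power of > 80% to detect a significant difference from the historical control".

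The treated side is more selected. Section 14.1.2.1 requires infusion before 180 days of age, symptoms, bi-allelic *SMN1* deletion, two *SMN2* copies and no c.859G>C modifier. Section 8.2 excludes tracheostomy, non-invasive ventilation averaging 6 hours a day or more, "or requiring ventilatory support while awake over the 7 days prior to screening", low oxygen saturation, signs of aspiration, and weight below the third percentile. Section 5.1 states that "Disease severity and clinical prognosis depends on the number of copies of survival motor neuron 2 gene".

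**The concern.** An ITT child cannot have died, had a tracheostomy or been on permanent ventilation before dosing, because any of these would have kept the child out of the trial. The protocol places no matching condition on the controls. A control who had an event before the age at which trial children are dosed could therefore count as a failure of a kind that no treated child can have. Fisher's test would credit that guaranteed event-free time to the product.

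This matters because the trial has one arm, survival is a co-primary endpoint, and the whole contrast rests on who the 26 controls are. The protocol fixes their number, matching factors and expected rate but omits the condition that would make the two groups start from the same point. The word 'age' could mean age at onset, at study entry or at dosing, and these readings give different control sets.

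**Working it through.** **Inputs from Section 14.2.** Treated survival 80%; control survival 25%; 26 controls; two-sided Fisher's exact test at 0.05; 15 ITT patients less 30%, so 15 × 0.7 = 10.5, i.e. 10 or 11 analysed. The case of 15 is shown for no exclusions.

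**Input not in the documents.** Let f be the share of controls with an event before the matched dosing age. It is an assumption, shown from 0 to 40%. The 25% is assumed to count these early events.

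**Step 1: the plan's own figure.** Exact enumeration over both binomials at 80% against 25% gives power of 81.9% (10 vs 26), 85.9% (11 vs 26) and 92.6% (15 vs 26). The claim of more than 80% reproduces.

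**Step 2: the comparable control rate.** Survival to 14 months among controls event-free at the dosing age is 0.25/(1 − f):

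- f = 10%: 0.25/0.9 = 27.8%
- f = 20%: 0.25/0.8 = 31.3%
- f = 30%: 0.25/0.7 = 35.7%
- f = 40%: 0.25/0.6 = 41.7%

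**Step 3: false survival win.** A product with no effect on survival would show the Step 2 rate in treated children, who are all event-free at dosing. It would be tested against 26 unconditioned controls at 25%. Probability of a significant result in favour of treatment:

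| f | 10 treated | 11 treated | 15 treated |
|---|---|---|---|
| 0 | 1.7% | 1.7% | 1.4% |
| 10% | 2.5% | 2.6% | 2.2% |
| 20% | 3.9% | 4.1% | 3.9% |
| 30% | 6.6% | 7.0% | 7.3% |
| 40% | 11.7% | 12.5% | 14.4% |

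With the planned 10 or 11 analysed, the error in the favourable direction reaches 2.5% at about f = 10%.

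**Step 4: the sitting gate.** Survival is tested only if sitting is significant. Against a null of 0.1%, one sitter among 15 is enough. For a product with no effect on sitting, the chance of that is 1 − 0.999^15 = 1.5%. The rates in Step 3 therefore apply only to a product that produces sitting without improving survival.

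**Step 5: power against comparable controls.** 80% treated survival, 26 controls all event-free at the dosing age:

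| f | Control rate | 10 treated | 11 treated | 15 treated |
|---|---|---|---|---|
| 10% | 27.8% | 76% | 81% | 89% |
| 20% | 31.3% | 68% | 75% | 84% |
| 30% | 35.7% | 57% | 65% | 75% |
| 40% | 41.7% | 42% | 51% | 61% |

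Power first falls below 80% at a control rate of about 26% (10 treated), 29% (11) or 34% (15). A rate of 26% corresponds to f = 1 − 0.25/0.26, about 4%.

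**Step 6: robustness at the expected effect.** 12/15 survivors remain significant against 10/26 controls (38%), but 13/15 are needed against 13/26. 8/10 is significant against 9/26 but not against 10/26.

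**The case against.** The strongest reply is that the protocol is silent rather than wrong. Section 14.1.1 claims comparability. If 'age' means age at entry or dosing, matched controls would already be alive at that age. Control selection may also be set out in the SAP or in a later protocol version: the text discussed here is version 2.0, and the file also carries part of a later version's summary of changes without its body. This stands as a limit on the wording. A reader might infer that survivor bias is built in, or that age and gender are certainly the only factors used. The documents do not support either statement; they show an open risk.

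A reader might also infer that a control number fixed in advance rules out matching to the children actually dosed. It does not, since 26 patients can be group-matched to the known entry range of under 180 days.

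It is tempting to treat the missing *SMN2* restriction as more bias towards treatment. Section 5.2 does not bear that out. Of 113 Type 1 patients, the 9 with one copy lived less than 11 months, while 8 of the 10 with three copies lived 33 to 66 months. One-copy controls would favour the treated arm and three-copy controls would work against it. As an illustration, suppose 25% of such a mix survived to 14 months: 113 × 0.25 = 28.25. Removing 8 three-copy survivors leaves at most 20.25/94 = 21.5% among two-copy patients, so restriction could lower the control rate. The Synopsis also ties its expectation of no sitting to two copies without the modifier, which suggests a similar set may have been meant for survival.

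Finally, f has no anchor in the documents, and quoting survival at 13.6 months of age does not prove that every patient was counted from birth. The sizes above are therefore conditional.

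**Conclusion.** The concern holds as a gap in the control definition. The protocol fixes 26 controls matched on gender and an undefined age, and does not require them to be event-free at an age matching dosing, while the treated children are selected that way. If early-event controls are included, the direction is towards treatment. The size depends on the assumed share: little at 10%, about 7% false wins at 30%, and 12 to 14% at 40%, for a product that produces sitting but not survival. For a product with neither effect the cap is about 1.5%.

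The power arithmetic is correct as stated. Its margin is thin with 10 analysed and disappears at a comparable control rate of about 26%. A result near the expected effect would be fairly robust.

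The unstated genotype of the controls is a separate comparability gap whose direction the documents leave open; it is not survivor bias.

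**What to change.** In Sections 14.2 and 14.3.2, define the age used for matching. Include only controls who are alive without permanent ventilation at an index age matching the dosing ages. Where the natural-history records hold the information, also require the ITT genotype (two *SMN2* copies, no c.859G>C) and the trial's ventilation and nutrition entry criteria. Run the same Fisher test on 14-month survival in that set, add a delayed-entry Kaplan-Meier analysis as sensitivity, and restate the power for the resulting control number and rate.

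The cost is re-selection within the natural-history data and a few sentences of text. Whether those data hold genotype and ventilation hours for each patient is not stated, so that part may be only partly feasible. The downside is possibly fewer than 26 controls and a lower stated power. If early-event controls are dropped and not replaced, 26 × (1 − f) leaves about 23, 21, 18 or 16 controls at f = 10, 20, 30 or 40%. Power at 80% treated survival is then 77/65/59/40% with 10 treated and 90/84/70/50% with 15.

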### 14.3. Efficacy Analysis

#### 14.3.1. General Considerations

This study will compare the activity of AVXS-101 administered IV versus the natural observational results from PNCR [21] in terms of functional independent sitting and survival rate. The ability to thrive and the ability remain independent of ventilatory support will also be assessed.

The analysis of the co-primary and co-secondary efficacy endpoints will be performed for the ITT and efficacy completers population. The analysis based on the ITT population will be considered as the primary analysis. In the case of missing data, observed data will be used for the analyses.

Unless otherwise specified, the baseline measurement is defined as the last non-missing measurement collected prior to or on the day of gene replacement therapy infusion (e.g., on or before Day 1 visit).

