### **8.3. Patient Withdrawal Criteria**

Patients may be discontinued from the study for the following reasons:

- Death
  - An autopsy will be requested for any patient who expires following participation in a gene replacement study as per the National Institutes of Health’s Guidelines for Research Involving Recombinant or Synthetic Nucleic Acid Molecules [25] (see Autopsy Plan in [Appendix 2](#))
- Failure to comply with protocol-required visits or study procedures for 3 or more consecutive visits that are not rescheduled, unless due to hospitalization
- Parent(s)/legal guardian(s) withdraws consent
- Investigator discretion

Early termination procedures should be completed within 14 days for any patient who prematurely discontinues the study for any reason, as indicated in [Appendix 1](#).

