### **9.2.2. Prohibited Medications**

Concomitant use of any of the following medications is prohibited:

- Drugs for treatment of diabetes, myopathy or neuropathy
- Therapy received with the intent to treat SMA (e.g., nusinersen, valproic acid)
  - Oral  $\beta$ -agonists must be discontinued at least 30 days prior to gene therapy dosing.
  - Inhaled  $\beta$ -agonists may be used to treat respiratory complications of SMA provided such medications are dosed at clinically appropriate levels
- Any investigational medication other than AVXS-101 is prohibited during the study
- Ongoing immunosuppressive therapy, plasmapheresis, immunomodulators such as adalimumab, or immunosuppressive therapy within 3 months of starting the study (e.g., corticosteroids, cyclosporine, tacrolimus, methotrexate, cyclophosphamide, IV immunoglobulin, rituximab)

Corticosteroid usage following completion of the prednisolone taper is permissible as part of routine clinical management. The use of corticosteroids in such circumstances should be documented appropriately as a concomitant medication, and the event precipitating its usage should be appropriately documented as an adverse event.

Should the use of corticosteroids (aside from inhaled corticosteroids for bronchospasm) be considered as part of care during the course of the prednisolone taper, this medical management should be discussed with the medical monitor.

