#### 14.1.2. Statistical Analysis Populations

##### 14.1.2.1. Intent-to-Treat Population (ITT)

The ITT population will consist of symptomatic patients with bi-allelic deletion mutations of *SMN1* (exon 7/8 common homozygous deletions) and 2 copies of *SMN2* without the known gene modifier mutation (c.859G>C) who receive an IV infusion of AVXS-101 at less than 180 days of age. The first three patients enrolled must meet the criteria for the Intent-to-Treat Population.

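### The observed-data rule lets ITT children with no recorded outcome leave the denominator, which can raise the 18-month estimates and change the survival decision

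*Protocol*

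**What the plan says.** Section 14.3.1 fixes the primary population, "The analysis based on the ITT population will be considered as the primary analysis", and then gives the only missing-data rule in the protocol: "In the case of missing data, observed data will be used for the analyses".

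Section 14.1.2.1 defines ITT by symptoms, *SMN1* and *SMN2* genotype, and being a child among those "who receive an IV infusion of AVXS-101 at less than 180 days of age". Completing follow-up is not a condition.

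Section 14.2 plans sitting with the "primary endpoint being in the range of 30% - 40%, a sample size of 15 patients that meet ITT criteria will be enrolled", "assuming approximately 30% of patients are excluded from analysis". It makes the same 30% assumption for survival.

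Section 8.3 allows discontinuation for death, consent withdrawal, investigator discretion, or "Failure to comply with protocol-required visits or study procedures for 3 or more consecutive visits that are not rescheduled" unless the child is in hospital. It asks for early-termination procedures within 14 days and for no later check of vital or ventilation status.

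Section 14.1.1.1 makes death or permanent ventilation the failure event of the survival co-primary. Sitting, thriving and ventilator independence are all assessed at 18 months of age. The one sensitivity analysis (Section 14.3.2) repeats the primary analysis in the efficacy completers population.

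**The concern.** An ITT analysis needs an outcome, or a rule for one, for every member of the population. Here the rule is to use what was observed. For a proportion, this most naturally means that a child without a value is in neither the numerator nor the denominator. The 30% in Section 14.2 points the same way: it is applied to 15 children who already meet ITT criteria, so it cannot stand for ineligibility.

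SMA Type 1 is progressive and fatal, so children who leave early may well be doing worse than those who stay. If so, dropping them raises the reported proportions. In a single-arm trial of 15 with a sitting null of 0.1%, the test is easily met and the estimated proportion carries most of the evidence. Survival is a comparison of small counts, where a few children can decide significance.

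**Working it through.** **Inputs.** From Section 14.2: 15 children meeting ITT criteria; about 30% excluded; sitting null 0.1%, true rate 30% to 40%, one-sided exact binomial test at 0.025; survival 80% against 25%, 26 controls, two-sided Fisher's exact test at 0.05. The number of controls alive at 14 months is not given. Since 0.25 × 26 = 6.5, I assume 6/26 or 7/26 and show both.

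**1. The plan's own figures.** 15 × 0.7 = 10.5, so 10 or 11 children are analysed. One sitter is enough to reject.
- n = 10: size 1 − 0.999^10 = 0.0100; power 1 − 0.7^10 = 97.2% at a 30% rate and 1 − 0.6^10 = 99.4% at 40%.
- n = 11: size 0.0109; power 98.0% and 99.6%.
- Survival, by exact enumeration against 26 controls: power 81.9% (n = 10) and 85.9% (n = 11).

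Both stated powers (> 90% and > 80%) are reproduced, with the reduced denominator built in.

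**2. The 18-month estimates.** If m of 15 children are unobserved and would all have failed, dropping them multiplies the proportion by 15/(15 − m): 1.07 for m = 1, 1.36 for m = 4, 1.50 for m = 5. With six sitters:
- all 15 counted: 6/15 = 40.0% (95% Clopper-Pearson 16% to 68%)
- 4 dropped: 6/11 = 54.5%
- 5 dropped: 6/10 = 60.0% (26% to 88%)

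**3. The sitting decision.** One sitter rejects while 1 − 0.999^n stays below 0.025. At n = 15 it is 0.0149, at n = 25 it is 0.0247, and at n = 26 it is 0.0257. So for n from 10 to 15 the decision is the same whether missing children are dropped or counted as failures.

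**4. The survival decision.** Two-sided Fisher p-values; the first of each pair is against 6/26, the second against 7/26.

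| Survivors | Events | Lost | Lost dropped | p | Lost counted as failures | p |
|---|---|---|---|---|---|---|
| 8 | 6 | 1 | 8/14 | 0.043 / 0.089 | 8/15 | 0.086 / 0.108 |
| 8 | 4 | 3 | 8/12 | 0.014 / 0.033 | 8/15 | 0.086 / 0.108 |
| 8 | 3 | 4 | 8/11 | 0.008 / 0.025 | 8/15 | 0.086 / 0.108 |
| 9 | 3 | 3 | 9/12 | 0.004 / 0.012 | 9/15 | 0.041 / 0.051 |
| 10 | 2 | 3 | 10/12 | 0.001 / 0.002 | 10/15 | 0.009 / 0.021 |
| 12 | 0 | 3 | 12/12 | < 0.001 / < 0.001 | 12/15 | 0.0008 / 0.0014 |

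With 8 survivors and 3 or 4 lost, the decision changes under both control counts. With 8 survivors and 1 lost it changes only at 6/26, and with 9 survivors only at 7/26. With 10 or more survivors it does not change.

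**The case against.** **Deaths.** A reader might infer that children who die vanish from every success rate. They do not. Under Section 14.1.1.1 a death before 14 months is an observed survival failure and stays in that denominator. The survival exposure comes from withdrawals and losses with unknown status.

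**The wording.** Section 14.3.1 does not say that a child leaves the denominator. Section 11.1 treats a milestone as achieved only when it is demonstrated and confirmed on video, so one can argue that an unassessed child simply has not achieved sitting. That is a fair reading for sitting, but the protocol nowhere states it as the rule, and the planned 30% exclusion works against it.

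**A survivor or completer analysis.** It is tempting to call the primary analysis this. The documents do not go that far: even the completers set (Section 14.1.2.2) keeps deaths and discontinuations due to adverse events. That set does not settle the matter either, since it changes who is included and brings no rule counting a missing outcome as failure.

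**Direction and likelihood.** Upward bias needs missing children to do worse than those observed; a child who withdraws while doing well biases the rate the other way. The 30% is a planning allowance. The summary of changes shows that it once also covered children who did not qualify for ITT, so it should not be read as a dropout forecast. The survival changes in the table lie well below the planned 80%. All of this stands and limits the size of the point.

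**Other SMA therapy.** A child who starts another SMA treatment and is assessed at 18 months has no missing value, so this rule does not govern that case. It should be raised separately.

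**Documents not seen.** The SAP may add detail, and the material includes part of a later amendment's change log without that amendment's Section 14. The rule is nevertheless stated in the protocol text at hand.

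**Conclusion.** The point holds in a limited form. The protocol states an observed-data rule that does not fit its own ITT definition. Withdrawn or lost children, and on a literal reading deaths before 18 months, can leave the denominator of the 18-month endpoints. Unknown status at 14 months can leave the survival test.

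The sitting decision is safe. Its estimate can rise from 40% to 55% or 60% with six sitters, if the full 30% are unobserved and would have failed. The survival decision can go from non-significant to significant with 8 known survivors and 3 or 4 lost, under either assumed control count. At 10 or more survivors, which includes the planned 12 of 15, it does not change.

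**What to change.** Replace the sentence in Section 14.3.1, and carry the change into the SAP, along these lines:

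> All treated ITT patients remain in the denominator of the co-primary and co-secondary analyses. A patient who has died, or who has no valid assessment at 18 months of age for any other reason, is counted as not having achieved sitting, thriving or ventilator independence. A patient whose status at 14 months of age is unknown is counted as not surviving in the primary analysis. An observed-case analysis is reported as a sensitivity analysis.

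Add to Section 8.3 that vital and ventilation status is collected to 14 and 18 months of age after discontinuation, where consent allows. Section 14.2 should then say what the 30% represents.

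The cost is a few sentences and a telephone or records check for the few children who leave. Estimates become slightly less favourable, and the rule is conservative when a lost child was doing well. Collecting status matters for power. If the full 30% had unknown status and counted as failures, survival power would fall to about 35% (10 observed) or 51% (11 observed). With status known for all 15 it is 92.6%.
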